Participants for **Aim 3** will be identified through the Apache surveillance system. During the routine follow-up visits that are part of the Apache surveillance system, Community Mental Health Specialists (CMHSs) who complete these follow-ups may approach participants they know to be potentially eligible (based on age and behavior, two pieces of information they gather as routine part of this follow-up) to see if they are interested in hearing about this study and participating. If the potential participant is interested in hearing about the study but is unsure about participation, the CHMS will note their contact info and make a plan with the person to follow-up to continue the recruitment process. If the potential participant is interested in participating in the study, the CMHS will either schedule a time to complete the eligibility screening or continue by having the potential participant complete the eligibility screening questions. Once screened, if the participant is eligible based on their responses, they will complete the informed consent process. For eligible participants who consented, the CMHS will then administer the remaining baseline assessment or schedule a separate time to complete the baseline. If the person is not eligible, the CMHS will convey that information to the person and inform them that they are not

eligible for the study but can continue to receive regular services through the Apache surveillance system.

2. Address any privacy issues associated with recruitment. If recruitment itself may put potential participants at risk (if study topic is sensitive, or study population may be stigmatized), explain how you will minimize these risks.

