Aim 1: A potential privacy issue associated with recruitment is that respondents may be identified as having participated in the study. We believe this will have little to no effect as people are being asked to speak about problems in general and not specific to themselves or any other individuals. Data collection will take place in private. For all participants, every effort, including password protected storage of identifying information and destruction of study files post study, will be taken to ensure that confidentiality is maintained. All data for analysis will be de-identified data. Participants will be asked to name additional *potential* participants using chained sampling methods, however, the recommending participant will initiate contact with this new individual, rather than Apache research staff, to respect their privacy.

Aim 2: N/A, there are no research participants for Aim 2.

Aim 3: Maintaining confidentiality is of the utmost concern. Adults for the RCT will be recruited through the Apache surveillance system. As current practice, individuals in the system are followed-up by case managers. Case management visits take place in a private location where the individual feels comfortable such as at a home or at an office. Case managers will ask about their interest in participating with this research at the end of the initial case management visit. Case managers will explain the nature of the study, the reason the person is being asked to participate, and nature of data gathering during a routine case management visit, following the aim 3 recruitment script (see recruitment materials). The Apache research team for this study consists of JHSPH-employed CMHSs who have deep experience in implementing the local Apache suicide surveillance and case management system.

B. Consent Process:

- 1. Describe the following details about obtaining informed consent from study participants. If a screening process precedes study enrollment, also describe the consent for screening.
 - a. Who will obtain informed consent, and their qualifications:

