Consent in this study will be obtained prior to any research-related participation. Apache Research Program Assistants (RPAs; above referred to as CHMSs in context of the Apache surveillance system, but who are known by both titles) who have been trained by JHU will obtain informed consent from participants. They will be trained in responsible conduct of human subjects research as a part of field training procedures. This will include training in the principle of respect for persons, protecting confidentiality, and the process of informed consent. All RPAs involved with data collection have been trained in human subjects research protections and have up to date CITI certifications, specifically, the human subjects training for field workers (JHSPH Human Subjects Research Basic Course), and abbreviated Good Clinical Practice slide set (Good Clinical Practice, Social/Behavioral Interventions).

b. How, where, and when the consent discussion(s) will occur:
 Informed consent will be obtained in a private location agreed on by the participant. Consent discussions will take place prior to the collection of any data. In the case of individuals recruited

[figure not shown]
at places of residence, individuals will be asked to identify a private location within their home. Written informed consent will be obtained for all participants.

During the consent process, the Research Program Assistant will ask prospective participants if they fully understand the consent process/forms. All participants will understand that participation is completely voluntary, acceptance or refusal will not influence their ability to participate in other Tribal or JHU services, and they can withdraw from study participation at any time. For **Aim 1** consent processes will happen at the time of the first visit if the potential participant is interested in the study. For **Aim 3**, the consent process will happen during the recruitment/eligibility screening process as described above and below in the "recruitment process" and "process you will use to determine whether a potential participant meets eligibility criteria" sections (i.e., private location, during the initial case management visit, unless otherwise requested by the potential participant).

c. The process you will use to determine whether a potential participant meets eligibility criteria:

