For **Aim 1**, participant eligibility will be determined during discussions with the CAB, Research Program Assistants and/or Baltimore based study staff. For Aim 3, participants will initially be identified by the Apache surveillance system. During the routine follow-up visits that are part of the Apache surveillance system, Community Mental Health Specialists (CMHSs) who complete these follow-ups may approach participants they know to be potentially eligible (based on age and behavior, two pieces of information they gather as routine part of this follow-up) to see if they are interested in hearing about this study and participating. If the potential participant is interested in hearing about the study but is unsure about participation, the CHMS will note their contact info and make a plan with the person to follow-up and continue recruitment. If the potential participant is interested in participating in the study, the CMHS will either schedule a time to complete the eligibility screening or continue by having the potential participant complete the eligibility screening questions (the eligibility screening consists of two brief screening measures, one the ACEs measure, the other a subset of questions from the Harvard Trauma Questionnaire; see data collection instruments). Once screened, if the participant is eligible based on their responses, they will complete the informed consent process. For eligible participants who consented, the CMHS will complete the initial contact form as part of the enrollment process, and either administer the rest of the baseline survey or schedule another visit to complete the baseline. See Figure 1 for a flowchart illustrating the eligibility screening process.

- d. Whether you will obtain a signature from the participant or will use an oral consent process: We will obtain a signature from the participant to document consent.
- e. Whether you will obtain a legally authorized representative's signature for adults lacking capacity:

N/A

f. If children are included in the study, if and how you will obtain assent from them:

N/A

g. If children are included in the study, how you will obtain permission for them to participate from their parent, legal guardian, or other legal authority (if child is in foster care or under government supervision):

N/A

- h. If you are seeking a waiver of informed consent or assent, the justification for this request: N/A
- Whether you will include a witness to the consent process and why:

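### Aim 3 screening asks the ACE and trauma questions before consent, against the plan's own consent rule, with no screening consent or waiver described

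*Combined protocol and SAP*

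**What the plan says.** Three sections of the combined protocol and SAP give the same Aim 3 sequence: V.A.1 (Recruitment Process), V.B.1.c (determining eligibility) and V.C.1 (Study Implementation). Each says: "Once screened, if the participant is eligible based on their responses, they will complete the informed consent process". Sections V.B.1.c and V.C.1 define the content: "the eligibility screening consists of two brief screening measures, one the ACEs measure, the other a subset of questions from the Harvard Trauma Questionnaire". People are approached for screening on the basis of what the surveillance follow-up already records: "based on age and behavior, two pieces of information they gather as routine part of this follow-up".

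The Consent Process section states a different rule. V.B.1.a: "Consent in this study will be obtained prior to any research-related participation". V.B.1.b: "Consent discussions will take place prior to the collection of any data". For Aim 3, V.B.1.b adds that "the consent process will happen during the recruitment/eligibility screening process as described above and below". The waiver item, V.B.1.h, reads: "If you are seeking a waiver of informed consent or assent, the justification for this request: N/A".

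**The concern.** The two sets of instructions cannot both be followed. A staff member who obeys V.A.1 breaks V.B.1.a and V.B.1.b, and the reverse.

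What is at stake is participant protection and a clear basis for holding the screening answers. The people approached have had suicidal thoughts, a suicide attempt, self-injury or a substance binge in the previous 90 days. The ACE module has 24 questions on childhood adversity. Section VII.A itself foresees that distressed respondents may disclose suicidal intent at screening. The staff who make the routine follow-up visit also offer the screening (V.A.1). The assurance that refusing has no effect on other services is part of the consent process in V.B.1.b, so in the written order it comes after the sensitive questions.

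**Working it through.** No arithmetic applies. The plan gives no figure on this point, and the check is a comparison of texts.

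1. **Order of steps.** V.A.1, V.B.1.c and V.C.1 agree: approach, screening questions, consent for those who qualify, then the rest of baseline. Three matching statements describe a procedure and are not a slip of the pen.

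2. **Are the screening answers routine data?** The plan names age and behaviour as the routine items used to decide whom to approach. It does not list the ACE or HTQ items among them. Both are Aim 3 eligibility measures (IV.A), and the ACE module has its own row in the Aim 3 assessment schedule (Table 2, V.C.4). They therefore fall within the data that V.B.1.b says must follow the consent discussion.

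3. **Does the Aim 3 sentence in V.B.1.b settle it?** It places consent within the recruitment and screening process and refers the reader to the sections describing that process. Those sections put screening first, so the sentence returns to the conflict without resolving it.

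4. **Is there a separate consent for screening?** The form asks for one: "If a screening process precedes study enrollment, also describe the consent for screening". The answer describes none. The consent-document table in V.B.2 lists two forms, one for Aim 1 and one for Aim 3, and no screening form.

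5. **Is there a waiver?** V.B.1.h is answered N/A.

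6. **Which measures are taken only before consent?** In Table 2 the ACE row carries one mark, in the first column. Intact rows such as the Trait Hope Scale leave that column blank and carry five marks after it, so the first column is Screening. On that reading the ACE module is scheduled once before consent and at none of the five later assessments. After consent, V.B.1.c mentions only the remainder of the baseline survey. The HTQ row appears to have six marks, a brief version at screening and then all five assessments, so the primary outcome is measured again after consent.

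7. **Effect on the trial comparison.** Randomisation follows consent and baseline (V.C.5.A), so both arms pass through the same screening step. The models in V.C.4 name gender and age as baseline characteristics and do not use the ACE score.

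**The case against.** The strongest reply is that the sequence is deliberate and disclosed. Three sections agree on it, the Aim 3 sentence in V.B.1.b points to it, and the two sentences promising consent first are general text for all aims that was not adapted. This may well explain how the conflict arose. It does not remove it, because the general sentences make no exception for screening and no waiver is claimed.

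A reader might infer that people are screened with no safeguards. The documents do not support that. Under V.A.2 the case manager explains the study, the reason for the approach and the nature of the data gathering, in private and from a script. Under V.A.1 only people who express interest are screened, and those found ineligible are then told that their regular services continue. Section VII.A covers disclosure of suicidal intent during screening and points to the safety protocol. What is missing at that moment is the written consent and its assurance about refusal.

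A reader might also infer that the ACE data could not be used, or that answers from people who fail screening are needed to report eligibility yield. Neither is in the documents. No section says that screening answers must be discarded, and the content of the Aim 3 consent form cannot be checked here. The feasibility analysis in V.C.4 relies on call notes and case-manager responses and defines no yield measure.

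The objection on timing has force. Sections I and III describe feasibility recruitment in the past tense, and V.C.4 says case managers have already commented on preliminary findings. Reordering the visit may come too late.

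**Conclusion.** The contradiction stands. As written, everyone screened for Aim 3 answers the ACE and HTQ screening items before consent, and people found ineligible are never consented. The plan neither describes a screening consent nor seeks a waiver. The number screened is not given; the feasibility target is 30 participants.

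The consequence is limited to consent and to the stated basis for holding screening answers. It would be wrong to read this as a bias in the randomised comparison or a defect in the HTQ primary outcome, for the reasons in steps 6 and 7 of the working. The point is worth correcting because the sensitive questions come first for a high-risk group and the remedy is cheap.

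The conclusion rests on two assumptions. One is that Table 2, broken in extraction, is read correctly; this bears only on the statement that ACE is measured once. The other is that the screening flowchart (Figure 1), the recruitment script and the consent forms, none of which could be seen, contain no separate consent for screening. If they do, the three screen-first sections and the consent sections still need to be brought into line.

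**What to change.** Choose one of two routes.

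- **Consent first.** Place the Aim 3 consent, or a short screening consent, ahead of the ACE and HTQ items in V.A.1, V.B.1.c and V.C.1, so that they agree with V.B.1.a and V.B.1.b. List any new form in V.B.2.
- **Screen first.** State and justify a waiver for screening in V.B.1.h, and correct V.B.1.a and V.B.1.b to match.

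Under either route, state whether screening answers from people who are ineligible or who decline are kept, and on what basis. If enrolment is complete, document which order was followed and the basis for using the screening data.

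The cost is an IRB amendment and, with consent first, a few minutes of consent time with people who prove ineligible.

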Update, January 2025: Since the initial award, and based on challenges navigating the COVID-19 pandemic to recruit participants and complete study visits, we received approval from the sponsor to transition the randomized control trial (Aim 3) to a feasibility study with a smaller sample size. In the feasibility study for Aim 3, we aimed to recruit n=30 participants and understand the feasibility of scaling this study at a larger size and understand the challenges of implementing this intervention with this population of adults experiencing suicide, self-injury, and substance use. The rest of the study design, aside from the sample size in Aim 3, remained the same throughout the project.

- B. Provide a sample size and a justification as to how you arrived at that number. If you use screening procedures to arrive at a final sample a table may be helpful.
 - Aim 1: We anticipate conducting free-listing, key informant interviews with approximately 30 respondents. This sample size is based on considerations in qualitative research theory regarding saturation, a point after which common themes and information from local respondents tend to converge.
 - Aim 2: We estimate having 8 team members (plus the PI) trained in the intervention and piloting the intervention with 8 non-research participants.

Aim 3: For the RCT, estimated Sample Size is N=100 across the two groups Sample size for this aim is based on powering our sample to detect clinically meaningful and statistically significant difference in posttraumatic stress symptoms (primary outcome) between the two groups at 6-month (24wks) post baseline (12wks intervention period; 12wk assessment period). With power set to 80% and the type-I error rate set to alpha = 0.05, with a minimum of three time points and assuming a correlation of 0.3 between timepoints, we would expect to need a total sample size of N=70 to detect a medium effect of (f=0.25). We further adjusted our sample sizes to account for a conservative estimate of 30% attrition based on previous common elements RCTs, which yielded a total sample size of N=100 across the two groups.

In the updated feasibility study for Aim 3, we aimed to recruit a sample size of N=30 participants, which was an achievable goal for the study timeline based on recruitment patterns post-COVID. It

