Aim 3: During the routine follow-up visits that are part of the Apache surveillance system, Community Mental Health Specialists (CMHSs) who complete these follow-ups may approach participants they know to be potentially eligible (based on age and behavior, two pieces of information they gather as routine part of this follow-up) to see if they are interested in hearing about this study and participating. If the potential participant is interested in hearing about the study but is unsure about participation, the CHMS will note their contact info and make a plan with the person to follow-up and continue recruitment. If the potential participant is interested in participating in the study, the CMHS will either schedule a time to complete the eligibility screening or continue by having the potential participant complete the eligibility screening questions (the eligibility screening consists of two brief screening measures, one the ACEs measure, the other a subset of questions from the Harvard Trauma Questionnaire; see data collection instruments). Once screened, if the participant is eligible based on their responses, they will complete the informed consent process. For eligible participants who consented, the CMHS will complete the initial contact form as part of the enrollment process, and either administer the rest of the baseline survey or schedule another visit to complete the baseline. After completing the baseline survey, participants will receive one snack box of approximately \$30 value. After the baseline assessment the person will be randomized to either receive My Pathway to Healing intervention immediately, in addition to case management, or to receive case management alone (standard of care) while being asked to wait for the intervention. To ensure equal distribution of certain characteristics, participants will be block randomized by index event (ideation, attempt, self-injury, or binge substance use) and gender (male or female) using a 1:1 allocation ratio within blocks. The Research Program Assistants who collect study assessments will not be blinded to the intervention allocation. Previous work with the WMAT community has taught JHCIH that it is helpful for establishing trust and promoting participation when the Research Program Assistants who collect the study assessments can work with the Research Program Assistants who deliver the interventions to communicate with the participant, instead of the participant developing two separate relationships with each an evaluator and interventionist. Additionally, the Research Program Assistants who collect the study assessments do so by preparing a mobile tablet with the survey questions and handing it to the participant to complete, as such we believe that unblinding them will not influence the assessments that are collected. Regardless of assignment, the surveillance system provides regular case management as the existing standard of care. See Figure 2 for details on participant flow.

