Aim 3 (RCT): Our main analysis will be done on the "intent-to-treat" sample. This study utilizes repeated measures which leads to a nested data structure: 5 repeated assessments (level-1), nested within individuals (level-2), and nested within providers (level-3). We will use mixed-effects regression models (MRMs), which accommodate variability in assessment number and spacing within and across participants, continuous and discrete outcomes, and varied patterns of change over time (e.g., quadratic). 41 Model Building & Estimation. Outcomes will be graphically and descriptively evaluated to determine the best distribution for modeling using "spaghetti plots" and boxplots of outcome scores at each time-point. We will compare the within subjects covariance structure using model comparison techniques, selecting the appropriate covariance structure based on model fit (AIC, BIC). Then, we will build our models using the approach described in Singer and Willett: 42 1) Model 1 will estimate the proportion of outcome variance at each level specified above; 2) Model 2 will add growth terms (linear, quadratic) to examine how scores on outcomes change over time; 3) Model 3 will add fixed-effect indicators to test for differences in outcomes by baseline characteristic (gender, age). 4) Model 4 will add intervention (0=Control; 1=My Pathway to Healing) and condition by time interaction terms. Intervention effects will be the difference in outcome scores over time between the two groups.

In the feasibility study for Aim 3, we adapted the analysis plan to better understand the context, study population, and goals of the intervention for scaling and implementation. The feasibility analysis plan involves reviewing the notes from weekly study progress calls regarding challenges and successes in implementing the intervention in this sample of participants in this setting, and case manager responses to similar prompts in the intervention and assessment data collection in REDCap. Case managers have provided additional insights into the feasibility of implementing and scaling when giving feedback on the study progress and preliminary findings.

Study Participants:

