Session summary forms: One for intervention participants and one for control participants, these forms are used to track the mental health and well-being of study participants on a week-to-week basis. The forms ask questions about details of the control/intervention visits, including when they took place, what (if any) referrals were made, potential adverse events reported, interruptions during the visit, etc. The intervention form also asks about which parts of the MP2H curriculum were delivered.

Participant monitoring form is a brief form administered at each session of the My Pathway to Healing intervention that assesses for symptoms of depression, anxiety, trauma substance misuse, and safety. This form informs adaptations and tailoring of the intervention content and can help those delivering the intervention in identifying risk.

5. Answer the following if they are relevant to your study design:

A. If the study has different arms, explain the process for assigning participants (intervention/control, case/control), including the sequence and timing of the assignment.

The study has different arms only for Aim 3. There will be an intervention (My Pathways to Healing) group and a control group. Eligible, participants will be block randomized by index event (suicide attempt, suicide ideation, self-injurious behavior, or binge substance use) and gender using a 1:1 allocation ratio within blocks to either receive My Pathway to Healing immediately or be asked to wait. Randomization will occur after informed consent to participate in the study and the baseline assessment has been completed. At that point, the Research Program Assistant will tell the participant that a person from the team will be in touch about either starting My Pathway to Healing or scheduling a next assessment visit. The study coordinator will then check the data and if assigned to My Pathway to Healing, facilitate the referral to one of the community mental health specialists, based on who has availability in their schedule and is in close proximity to where the participant lives. If assigned to the wait-control group, the Research Program Assistant will schedule the next assessment visit with the participant through a follow-up call or visit.

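### Index event is a randomisation factor but is missing from the full-size mixed model; if it is prognostic, the standard error of the 24-week arm difference is overstated by a few per cent

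*Combined protocol and SAP*

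**What the plan says.** Two sections give the same allocation scheme. Section V.C.1 (Study Implementation, Aim 3) says "participants will be block randomized by index event (ideation, attempt, self-injury, or binge substance use) and gender (male or female", and section V.C.5.A says "block randomized by index event (suicide attempt, suicide ideation, self-injurious behavior, or binge substance use) and gender". Both set a 1:1 ratio within blocks. Four index events by two genders make eight strata.

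The Aim 3 analysis in section V.C.4 builds a mixed model in four steps. On baseline characteristics it says "Model 3 will add fixed-effect indicators to test for differences in outcomes by baseline characteristic (gender, age". Then "Model 4 will add intervention (0=Control; 1=My Pathway to Healing) and condition by time interaction terms". Index event appears in none of the four models, and no reason is given. Gender, the other randomisation factor, is included.

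The plan describes its target contrast in two ways. Section III.B sizes the trial on a difference "between the two groups at 6-month (24wks) post baseline", a comparison of levels. Section V.C.4 says "Intervention effects will be the difference in outcome scores over time between the two groups" and does not say which model term is the primary test.

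For the later N=30 feasibility study, section V.C.4 describes a review of progress-call notes and case manager responses. It describes no regression.

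**The concern.** Stratified blocks balance index event across the arms, so variation due to index event largely drops out of the true sampling error of the arm difference. A model without the factor does not know this. It leaves that variation in the person-level variance and reports an SE larger than the actual spread of the estimate. Confidence intervals are then too wide, the test rejects less often than its nominal level, and some of the power that stratification could have delivered is lost.

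The plan treats index event as important enough to balance and then makes no analytic use of it. A prognostic link is most plausible for two secondary outcomes, the SIQ and the ASSIST, because they measure behaviours that define the strata. Nothing is said about a link with the primary outcome.

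**Working it through.** **1. The plan's own sample size.** Inputs from section III.B: f=0.25, three time points, correlation 0.3, alpha 0.05, power 80%, attrition 30%. For the between-group test in repeated measures, with m time points and correlation ρ,

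λ = f²·N·m / (1+(m−1)ρ) = 0.0625 × 70 × 3 / 1.6 = 8.20, with 1 and 68 df.

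Power is 80.6% at N=70 and 79.4% at N=68. Then 70/(1−0.30) = 100. Both stated figures reproduce. The formula tests a level (the mean over visits); the within-between interaction version would give N=38. So the sizing rests on a level contrast. For two equal groups, f=0.25 is 0.5 SD.

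**2. SE of the 24-week difference, closed form.** Assumptions: visits at weeks 0, 12, 16, 20 and 24; total variance 1; equal correlation 0.3 between visits, so person-level variance is 0.3 and within-person variance 0.7; 35 per arm; complete data. Let R² be the share of single-visit variance due to index event, constant over visits. It is part of the person-level 0.3, so under this structure R² cannot exceed 0.3. The documents do not give R².

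Let h be the leverage of week 24 in the fitted time curve.

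- Without index event: SE = √[2(0.3 + 0.7h)/35]
- With index event: SE = √[2(0.3 − R² + 0.7h)/35]

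For linear time, the mean week is 14.4, the sum of squares is 339.2, and h = 1/5 + 9.6²/339.2 = 0.472. So 0.3 + 0.7h = 0.630. For quadratic time h = 0.811 and the sum is 0.867. For time as categories h = 1 and the sum is 1.

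| Time | SE without, N=70 | With, R²=5% | With, R²=10% | Ratios |
|---|---|---|---|---|
| Linear | 0.190 | 0.182 | 0.174 | 0.960, 0.917 |
| Quadratic | 0.223 | 0.216 | 0.209 | 0.971, 0.941 |
| Categories | 0.239 | 0.233 | 0.227 | 0.975, 0.949 |

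The ratios do not depend on N.

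**3. The condition-by-time contrast.** With linear time, the SE of the arm difference in change from week 0 to week 24 is √[2 × 0.7 × 24²/339.2 / 35] = 0.261. Person-level variance does not enter, so a constant index-event effect changes nothing.

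**4. Does the reported SE match the true spread?** This was simulated with no true effect: N=100, 30% monotone dropout, eight strata, blocks of 4, index-event mix 40/20/15/25%, random-intercept REML, 2,000 trials per row. Block size and mix are assumptions, and the provider level was left out. Approximate power at 0.5 SD is Φ[(0.5 − 1.96 × reported SE)/actual SD].

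| Arm-by-time | R² | Reported SE / actual SD, without | With | Type I, without | With | Power, without to with |
|---|---|---|---|---|---|---|
| Linear | 5% | 0.1773/0.1698 = 1.04 | 0.1712/0.1692 = 1.01 | 4.70% | 5.40% | 82% to 83% |
| Linear | 10% | 0.1774/0.1648 = 1.08 | 0.1644/0.1625 = 1.01 | 3.95% | 5.40% | 82% to 86% |
| Quadratic | 5% | 0.2155/0.2116 = 1.02 | 0.2104/0.2111 = 1.00 | 4.75% | 5.45% | 64% to 66% |
| Quadratic | 10% | 0.2155/0.2076 = 1.04 | 0.2049/0.2058 = 1.00 | 4.55% | 5.50% | 65% to 68% |

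The Monte Carlo error of a 5% rejection rate is √(0.05 × 0.95/2000), about 0.5 points, so the rates with index event are compatible with 5%. For the change contrast, reported SE over actual SD was 0.99 throughout, with or without index event.

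**5. Price if index event is not prognostic (R²=0).** In a separate simulation of a single 24-week outcome, adding four-level index event widened the confidence interval by 0.1-0.2% at N=100 and 0.3-0.5% at N=70.

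**The case against.** The strongest reply is that the effect in section V.C.4 is carried by condition-by-time terms, which are untouched. That stands for a constant index-event effect. A reader might infer that the omission weakens whatever test the plan runs; it does not. It bears on a level difference, which is what section III.B sizes on, and section V.C.4 never says which contrast is primary.

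A second reply is that Aim 3 became an N=30 feasibility study with a review of notes. That also stands. A reader might carry the loss over to that study because section I says the rest of the design was unchanged, but no mixed model is described for it. The point is confined to the full-size model, which is still in the current text.

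Third, the link with the primary outcome may be weak. Everyone enrolled must have elevated post-traumatic stress, and a participant may have several of the qualifying behaviours, so one index label separates overlapping groups. This is fair, and it is why R² is shown as an assumption.

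Larger figures are available: at R²=20% with linear time the SE falls by 17% (ratio 0.826). But that has a four-level label explaining 0.20/0.30, or two thirds, of all stable differences between people, under the more favourable time model. The plan allows quadratic growth, and nothing in the documents supports an R² that high.

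Finally, a reader might take the mismatch as a source of bias or false positives. The direction is the opposite: balance protects the estimate, and the test without the factor is conservative.

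**Conclusion.** The point holds as a small, conditional loss of efficiency. For a 24-week level difference in the full-size model, omitting index event overstates the SE if index event is prognostic. At an assumed R² of 5-10%, adding it lowers the SE by about 3-6% (quadratic time) or 4-8% (linear time). In the simulation with dropout the gain in approximate power is about 1 to 4 percentage points.

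The size rests on R², equal correlation of 0.3, an index-event effect constant over visits, and assumed block size and event mix. Severity is minor.

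**What to change.** In section V.C.4, list index event and gender (the randomisation factors) and age as fixed effects in Models 3 and 4. In the same place, state whether the primary test is the 24-week difference of section III.B or the condition-by-time term. If it is the latter, the index-event main effect changes nothing, and an index-event-by-time term is worth adding only if index event is expected to predict change.

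The change costs 3 degrees of freedom (and 3 more for each time term that index event is crossed with). It needs no new data, because index event must be known before a participant can be randomised.
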